2.1 Recruitment

Patients will be identified for recruitment via two routes:

1. Patients with an established diagnosis of inflammatory bowel disease who have been identified as being 'at risk' by either their secondary care doctor or GP and now require endoscopic assessment for ongoing disease symptoms but are unable to access endoscopy services urgently.
2. Patients presenting directly to their GP practice with symptoms of anorectal disease (e.g. rectal bleeding or pain) or symptoms that would warrant referral to a hospital under a 2WW appointment according to NICE criteria

All patients will be provided with written information about the study and an online website will be created to provide this information. The study aims to recruit 100 patients into the pilot study.

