2.2 Quality assurance and training

All clinicians will be provided with an onboarding protocol and a LumenEye SOP for standardised use, which include recommendations for use during the Covid-19 pandemic will be created. All clinicians performing investigations with the LumenEye will undergo training and quality assurance assessment. The first 5 procedures will be performed with a proctor to ensure that this is performed safely using appropriate PPE according to Public Health England Recommendations.

The primary study site will be based at Imperial College NHS trust which is a recognized National Bowel Cancer Screening (NBCS) Centre of excellence. The Imperial endoscopy suite performs over 10,000 endoscopic procedures each year. Additional primary sites will be located at:

King's College Hospital NHS Foundation Trust- [name]
NHS Frimley Health Foundation Trust – [name]

All patients enrolled into the study will be asked to have either an enema or glycerine suppository prior to the examination. They will be examined by the primary care physician in the clinic as per a standard rigid sigmoidoscopy assessment. Physicians may take biopsies if required but only if the physician feels this is warranted for clinical use. There is no requirement for research specimens in this study.

All doctors using the LumenEye will be asked to record images showing standard anatomical locations including:

1. The rectosigmoid junction
2. Each rectal haustral fold
3. Exit from the rectum.

Videos will also be recorded for any pathology identified.

Virtual clinics will be coordinated by the CI and Co-Is. During these clinics, a secondary care physician or surgeon will be available to discuss the case with the GP. These could be performed in real time with the patient present during a live examination or they could be performed retrospectively as part of a multidisciplinary team meeting.

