2.3 Analysis

Clinicians will be asked to provide qualitative feedback data with each use concerning device performance. This will be in the form of a short questionnaire, split into technical performance, views achieved, diagnostic yield, quality of the telemedicine interaction, patient outcome (discharged or referred to formal endoscopy) and adverse events.

Local users of the LumenEye system will undergo nasal swab assessments every 4 weeks for a covid-19 PCR test to ensure staff safety is maintained during the study. If a swab tests positive, the physician will be asked to follow standard PHE advice on isolation, contact tracing and further treatment.

All LumenEye devices will undergo at least one random post-cleaning swab test for Covid-19 to confirm the Tristel Trio cleaning system sufficiently eradicates SARS-COV-2 from the LumenEye. (An analysis of this has been performed outside of the study which confirms the efficacy of the Tristel Trio system against SARS-COV-2).

Patient feedback will be requested through a validated questionnaire..

All clinicians providing advice and guidance via CHiP will be asked to provide data on the quality of the views, the stability of the platform and to provide information on the diagnosis. For flare patients, both clinicians will be asked to report Mayo flare scores based on observed

data. For adenomas, clinicians will be asked to report anatomical location, morphology, and Paris endoscopy assessment scores. All data pertaining to follow up colonoscopy or flexible sigmoidoscopy will be used as a comparator group for a diagnostic sensitivity / specificity analysis.

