2.4 Study Outcome Measures

Primary outcome:

Both safety and patient and clinical acceptance of the LumenEye device with specialist consultation over the CHiP platform.

Secondary outcomes:

1. To establish the clinical utility of the CHiP software system for performing remote telemedicine assessment of the rectum and colon.
2. To provide pilot data for the diagnostic accuracy of the LumenEye system for colitis severity, cancer, rectal polyps and benign disease of the rectum and anus

3 Participant Entry

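### The protocol describes no record of the local clinician's diagnosis or intended disposition before CHiP contact, and no required status for each CHiP session, so the consultation's effect on decisions cannot be isolated

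*Combined protocol and SAP*

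**What the plan says.** Section 2.4 lists as the first secondary outcome "To establish the clinical utility of the CHiP software system" for remote telemedicine assessment. Neither section 1.3, section 2.4 nor section 6 turns this into a measurable endpoint. Section 6 calls the study a feasibility study and names only standard univariate methods.

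Section 2.3 describes two sources of clinician data that bear on CHiP:

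- **Local user, at each use.** "Clinicians will be asked to provide qualitative feedback data with each use concerning device performance". Besides technical performance, views and diagnostic yield, this questionnaire covers "quality of the telemedicine interaction, patient outcome (discharged or referred to formal endoscopy) and adverse events".
- **Remote specialist, when advice is given.** "All clinicians providing advice and guidance via CHiP will be asked to provide data on the quality of the views", along with "the stability of the platform and to provide information on the diagnosis". In flare patients, both clinicians give a Mayo score.

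Section 2.2 says that in the virtual clinics "a secondary care physician or surgeon will be available to discuss the case with the GP", and that this may happen live during the examination or afterwards at a multidisciplinary meeting. Section 2.1 gives the target: "The study aims to recruit 100 patients into the pilot study".

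**The concern.** A consultation platform has clinical utility partly because it changes what is done. To see that, one needs to know what the local clinician would have concluded and done alone, and what was concluded and done after the specialist's input. The described data contain only the second of these for disposition. A discharge the local clinician would have made anyway looks the same as one the specialist made possible.

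This reaches beyond a secondary outcome. The main hypothesis (Study Summary and section 1.2) includes a reduction in endoscopy referral. The study has no comparison arm, so a before-and-after record within each examination is the simplest way to show what CHiP contributes to that reduction. An intention not written down at the time cannot be reliably reconstructed later.

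A second, smaller gap concerns reliability. Platform stability is requested from specialists who gave advice. A session that never connected, or for which no specialist was free, has no such person. The primary outcome is framed as acceptance of the device with specialist consultation over CHiP, so the number of patients who actually had that consultation needs to be known.

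**Working it through.** The plan states no figure for CHiP utility or platform success, so there is nothing to reproduce. The main check sets what the question needs beside what section 2.3 describes.

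| Needed | Described in section 2.3? |
|---|---|
| Local diagnosis before specialist input | No. Diagnostic yield is listed, without timing relative to CHiP |
| Intended discharge or referral before specialist input | No |
| Disposition | Yes, on the per-use questionnaire; not stated whether it precedes or follows the consultation |
| Specialist's diagnosis | Yes |
| Whether advice changed anything | No |
| View quality, platform stability | Yes, from specialists who gave advice |
| Quality of the interaction | Yes, from the local user at each use |
| Status of each session (completed, failed, no specialist, not sought) | Not required |
| Mode (live or retrospective) | Not required |

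The paired Mayo scores do not fill the gap. They are confined to flare patients and measure agreement, not change in management. No order is set, so in a live session the local score may already reflect the specialist's view.

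**Illustration of the denominator (assumed inputs).** Let f be the share of attempted sessions that fail, and p the proportion rated good among completed sessions. With failures counted as non-success, success over all attempts is p × (1 − f). With p = 0.90:

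- f = 5%: 0.90 × 0.95 = 85.5%
- f = 10%: 0.90 × 0.90 = 81%
- f = 20%: 0.90 × 0.80 = 72%
- f = 30%: 0.90 × 0.70 = 63%

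In counts, at f = 20% of an assumed 100 attempts: 72/80 = 90% (exact Clopper-Pearson 95% CI 81.2% to 95.6%) against 72/100 = 72% (62.1% to 80.5%). Both p and f are assumptions.

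**What the added item could deliver (assumed rates).** If all 100 patients had a consultation and the change in disposition were recorded, the exact 95% intervals would be:

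- 10 of 100 changed: 4.9% to 17.6%
- 20 of 100 changed: 12.7% to 29.2%
- 30 of 100 changed: 21.2% to 40.0%

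Fewer consultations would widen these. Section 2.2 makes a specialist available but does not say that every patient has a session.

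**The case against.** The strongest reply is that the outcome concerns utility for performing remote assessment, which can be read as asking whether remote viewing works rather than whether it changes decisions. On that reading section 2.3 collects relevant data: views, stability, the specialist's diagnosis, paired Mayo scores, and follow-up endoscopy as a comparator. For a feasibility pilot that may be thought enough. This stands to the extent that those aspects can be described. It does not cover what the consultation adds to the discharge-or-refer decision, which the main hypothesis brings in.

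A reader might also infer that CHiP ratings come only from specialists, so that failed sessions disappear. The documents do not support that. The local questionnaire is due at each use and includes technical performance and the quality of the telemedicine interaction, so a lost link could be reported there. Images are stored, so a failed live link could still be followed by a retrospective review and a specialist form. Nor does the plan commit to a completed-sessions denominator; it states none. What remains is that failures need not be recorded or counted, and that nothing in the plan separates an item left blank, one not applicable and one rated poor.

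The questionnaires themselves are not in the documents, and section 2.3 lists domains rather than items. The finding is therefore that the protocol describes no such item, not that no form contains one.

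Finally, in a live session the specialist may be watching from the start, so a provisional opinion may not be independent. That is fair, and is a reason to analyse the two modes separately.

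**Conclusion.** The concern holds in a limited form. As described, the study can report how well CHiP sessions looked and worked to those who used them, but it cannot separate the specialist's effect on diagnosis or disposition from the local clinician's own decision. For decision change there is no described numerator, so no proportion can be estimated. For platform success, the numerator and denominator are both left open.

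It would go too far to say that clinical utility cannot be established at all, since several feasibility aspects of it can be described. It would also go too far to say that the plan will report an inflated success rate. The gap between 90% and 72% depends on an assumed failure rate of 20%, and the documents give neither a failure rate nor a denominator.

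This is a worthwhile, inexpensive improvement rather than a flaw that undermines the study. The conclusion rests on section 2.3 being a fair account of what will be collected.

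**What to change.** On the questionnaire already completed at each use, add:

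1. The local clinician's provisional diagnosis and discharge-or-refer intention, entered before specialist input, and the final ones after it. In live sessions, take the provisional entry before the specialist comments, and note that it may be less independent.
2. CHiP mode: live or retrospective.
3. CHiP status: completed, attempted and failed, no specialist available, or not sought.

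In sections 2.4 and 6, define the CHiP utility measure as the proportion of consultations in which diagnosis or disposition changed. Report it with the direction of change and an exact 95% CI, separately for live and retrospective sessions. Report platform success over all attempted sessions, with failures as non-success, and give the counts of sessions with no specialist available and sessions not sought.

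The cost is a few more tick-boxes on an existing form, with no extra staff or procedure. The platform success figure may come out lower, and the before-and-after contrast will be less clean in live sessions. The resulting estimates would also serve the power calculation for future studies that section 6 gives as a purpose.

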1.1.4 LumenEye and CHiP

The intervention: The LumenEye X1 (SurgEase Innovations Ltd, UK) is a CE Marked novel point of care rigid digital endoscope which provides High-Definition views of the rectum up to 20cm from the anal verge. It permits endoscopic biopsy under view (figure 1) and maintains pneumorectum sufficiently with as little as 100ml of air. Air delivery is in a closed system thereby significantly reducing aerosol transmission relative to formal endoscopy. This feature is particularly attractive in the current Covid-19 pandemic. A removable disposable manifold and a chemical clean with Tristel™ Trio is the only requirement for reprocessing

which is more cost-effective than automated washing & sterilisation. All images and videos are displayed on a HD screen, supplied alongside the scope, which can be captured and stored securely on the cloud platform (called CHiP, Figure 2) which allows retrospective review of images and data taken during rectoscopy from any device. The technology permits high quality endoscopy at the bedside and outside of traditional tiers of care which is particularly attractive during the current Corona pandemic. An additional feature of CHiP includes telemedicine functionality with live video sharing of the camera feed; a proctor can be invited over WIFI into a session who can then view the live feed from the scope and offer advice and guidance. The technology can offer cost-effective, immediate tumour visualisation, critical measurement, opportunity for biopsy and virtual diagnostic support.

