1.2 Rationale for current study

The LumenEye scope and CHiP platform will be piloted in a number of clinical settings including remote colorectal clinics. The rationale is to perform an initial pilot study to determine the clinical utility of the LumenEye device for use in primary and secondary care settings. The main hypothesis is that digital rectoscopy is safe and acceptable to clinicians including general practitioners and can significantly reduce the burden of endoscopy referral to and within secondary care centres.

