3.2 Inclusion Criteria

- Patients aged 18 and over
- Patients with any of the following:
 - Positive Faecal occult blood test / Faecal immunochemical test (FIT)
 - Positive faecal calprotectin.
 - Established history of polyps and/or adenomas
- 2WW patients referred to a colorectal clinic
- Known IBD patients with flare symptoms
- Patients with a suspected new diagnosis of IBD

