4.2.3 Contact details for reporting SAEs

Email: [contact]
Please send SAE forms to: [name], Department of Surgery and Cancer,
[name]
[name]

5 Assessment and Follow-up

We will record clinical outcome data in patients with a new diagnosis of IBD or colon cancer, and we will record if they underwent medical therapy, surgery or endoscopic therapy. The aim is to determine if the LumenEye improves the time to diagnosis and treatment, and ultimately outcome. The study will end when the 100th patient has been assessed and undergone any further investigation warranted by their presentation. Any incidental findings will be noted on the case report form and investigated as per the usual clinical pathways.

Data and all appropriate documentation will be stored for a minimum of 10 years after the completion of the study, including the follow-up period.

6 Statistics and data analysis

This is a feasibility study. The aim is to establish whether the device is acceptable and to establish the initial diagnostic performance of this device. This data will be used to form the basis of a power calculation for future studies. All data will be analysed using SPSS v. 20 and will be analysed using standard univariate statistical models.

7 Regulatory issues

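### The comparator endoscopy is reached partly through the LumenEye assessment and may be read with knowledge of it, or by the patient's own CHiP adviser, so sensitivity and specificity may both be inflated

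*Combined protocol and SAP*

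**What the plan says.** - **Comparator.** Section 2.3 says that "All data pertaining to follow up colonoscopy or flexible sigmoidoscopy will be used as a comparator group" "for a diagnostic sensitivity / specificity analysis". This serves the second secondary outcome in section 2.4: pilot accuracy data for colitis severity, cancer, polyps and benign disease.
- **Route to it.** The clinician questionnaire in section 2.3 records "patient outcome (discharged or referred to formal endoscopy" at each LumenEye use. Section 1.2 expects that the device "can significantly reduce the burden of endoscopy referral to and within secondary care centres". Section 5, however, has patients followed until they have "undergone any further investigation warranted by their presentation", and section 3.2 admits "2WW patients referred to a colorectal clinic".
- **Who sees the LumenEye result.** Section 1.1.4 says CHiP permits "retrospective review of images and data taken during rectoscopy from any device". Section 2.2 has a hospital physician or surgeon discuss the case with the GP, either live or later at a multidisciplinary meeting.
- **Who rates the index test.** Under section 2.3 the CHiP adviser gives a diagnosis, and for flare patients both clinicians give a Mayo score.
- **Size and analysis.** Section 2.1: "The study aims to recruit 100 patients into the pilot study". Section 6 plans univariate analysis in SPSS and says the data will support a power calculation for later studies.

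The text available does not say who performs the comparator endoscopy, when its findings are recorded, or what that person may have seen beforehand.

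**The concern.** An accuracy estimate needs a reference reading made independently of the index reading. As written, the plan allows two departures from that.

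1. **Index-aware reading.** A referral normally carries its reason, and the LumenEye images and scores sit on a shared platform. An endoscopist who knows where a lesion was seen will look there, and one who knows the Mayo or Paris grade may anchor on it.
2. **Same-person reading.** The adviser is a hospital physician or surgeon and could also be the endoscopist. One person would then supply both an index rating and the reference rating.

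In both cases it is the yardstick that moves towards LumenEye. Subjective grades are the most exposed. What is at stake is a secondary outcome, but section 6 intends these figures to size the next study, and optimistic accuracy could make that study too small.

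**Working it through.** The plan has no figure to reproduce. It gives 100 patients, with no expected accuracy, prevalence or verification rate. The check therefore shows direction and possible scale only.

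**Inputs.** From the documents: N = 100 (section 2.1). Assumed: true sensitivity Se = 0.80; specificity Sp = 0.90; prevalence p = 0.30 (0.10 and 0.50 as alternatives); every LumenEye-positive patient verified (v1 = 1); a share v0 of LumenEye-negative patients verified; a share q of discordant comparator readings altered to match LumenEye.

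**Expected counts before any influence on the reading**

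- TP = N·p·Se·v1
- FN = N·p·(1−Se)·v0
- FP = N·(1−p)·(1−Sp)·v1
- TN = N·(1−p)·Sp·v0

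**After influence:** TP + q·FP, TN + q·FN, FP·(1−q), FN·(1−q).

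| Case (p = 0.30) | TP | FN | FP | TN | Se | Sp | Agreement |
|---|---|---|---|---|---|---|---|
| All verified, independent reading (v0 = 1, q = 0) | 24 | 6 | 7 | 63 | 0.800 | 0.900 | 0.870 |
| Influenced reading, q = 0.25 | 25.75 | 4.5 | 5.25 | 64.5 | 0.851 | 0.925 | 0.903 |
| Influenced reading, q = 0.50 | 27.5 | 3 | 3.5 | 66 | 0.902 | 0.950 | 0.935 |
| Selective referral, v0 = 0.5, q = 0 | 24 | 3 | 7 | 31.5 | 0.889 | 0.818 | 0.847 |
| Selective referral, v0 = 0.3, q = 0 | 24 | 1.8 | 7 | 18.9 | 0.930 | 0.730 | 0.830 |
| Selective referral, v0 = 0.1, q = 0 | 24 | 0.6 | 7 | 6.3 | 0.976 | 0.474 | 0.799 |
| Both, v0 = 0.3, q = 0.25 | 25.75 | 1.35 | 5.25 | 19.35 | 0.950 | 0.787 | 0.872 |

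**Reading the table**

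- Influenced reading alone raises sensitivity and specificity together. For q = 0.25: 25.75 / 30.25 = 0.851 and 64.5 / 69.75 = 0.925.
- Selective referral alone raises sensitivity and lowers specificity. For v0 = 0.3: 24 / 25.8 = 0.930 and 18.9 / 25.9 = 0.730. The reading is fully independent in that row, so masking leaves this bias untouched.
- With both (v0 = 0.3, q = 0.25), overall agreement against its true value is 0.828 against 0.890 at p = 0.10, 0.872 against 0.870 at p = 0.30, and 0.902 against 0.850 at p = 0.50. The net sign changes with prevalence.

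**Consequence for the next study.** Suppose it is sized for the confidence-interval width of sensitivity, so that the number of diseased patients is proportional to Se(1−Se). The true value gives 0.80 × 0.20 = 0.160. The influenced values give 0.851 × 0.149 = 0.127 and 0.902 × 0.098 = 0.088. The planned number would then be 0.127 / 0.160 = 79% or 0.088 / 0.160 = 55% of what is needed.

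**The case against.** The strongest reply is that silence is not exposure. Section 1.1.4 describes what the platform can do; it does not say that the follow-up endoscopist has access or looks. No section says that the adviser performs the endoscopy. The study-outline figure is not reproduced in the text available, and neither the device SOP nor the case report form is included, so a safeguard could sit there. This stands: the point is a gap in the written plan, not evidence that readings will be contaminated.

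A reader might infer three stronger things that the documents do not support.

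- *That LumenEye is the only route to the comparator.* Section 5 ties further investigation to presentation, section 3.2 admits patients already on the two-week-wait pathway, and the first recruitment route in section 2.1 takes patients who already need endoscopic assessment. The masking gap nevertheless applies whatever the route.
- *That agreement with endoscopy is inflated as a matter of fact.* Selective referral pulls specificity down and can pull agreement down, so the net direction depends on values the plan does not give.
- *That a figure can be put on inflated Mayo agreement with endoscopy.* The plan names sensitivity and specificity, and asks for Mayo scores only from the LumenEye user and the adviser. Accuracy for colitis severity does need some comparator grade, but no agreement statistic against endoscopy is specified.

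It is also fair that this is secondary pilot data, and that comparator endoscopists may be outside the study team, so any form is a real request of them. Both limit the weight of the point. Neither closes the gap, because awareness that is not recorded at the time cannot be reliably reconstructed later.

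**Conclusion.** The point holds as a risk that the plan leaves open. The comparator is obtained partly on the basis of the LumenEye assessment, may be read with knowledge of it, and may be read by someone who has already rated the index test. That may inflate sensitivity and specificity together, most for Mayo and Paris grades.

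The size is not estimable from the documents. The range of 0.85 to 0.90 for sensitivity and 0.93 to 0.95 for specificity rests wholly on the assumed true accuracy, prevalence, full verification and 25% to 50% of discordant readings following LumenEye. Selective referral is a distinct bias that needs its own reporting, and the combined direction is unknown. Safety and acceptance, the primary outcome, are not affected. The change is worth making because the accuracy figures feed a later power calculation and the remedy is cheap.

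**What to change.** Add to section 2.3:

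1. Clinical findings needed for care are passed on as usual. The endoscopist records rectal findings and any Mayo or Paris score before opening CHiP images or LumenEye scores.
2. The comparator form has two tick-boxes: whether the endoscopist knew the LumenEye result, and whether they were that patient's CHiP adviser.
3. Accuracy is reported for all verified patients. A sensitivity analysis leaves out comparators read by the patient's own adviser, and results are also shown by awareness. Adviser-read comparators stay in the main analysis, because the verified group may already be only part of 100 patients and the extent of overlap is unknown.
4. The report gives the numbers of LumenEye-positive and LumenEye-negative patients who had the comparator, so that selective referral can be seen.

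**Cost.** One short extra form, possibly for clinicians outside the study team, and small subgroups in the split results. **What remains.** Detection of a lesion already named in the referral stays partly unmasked. Item 4 exposes selective referral but does not correct it.

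### Colitis severity is a graded target, but the only accuracy analysis named is a yes/no one, with no cut-point stated and no matching score required from the follow-up endoscopy

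*Combined protocol and SAP*

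**What the plan says.** Section 2.4 (Study Outcome Measures) lists, as secondary outcome 2, pilot data on "diagnostic accuracy of the LumenEye system for colitis severity, cancer, rectal polyps" and benign disease. Colitis severity is therefore one of four accuracy targets.

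Section 2.3 (Analysis) sets out the measurement: for flare patients, "both clinicians will be asked to report Mayo flare scores". In context these are the clinician using the LumenEye and the clinician advising over CHiP. For the comparator it says: "All data pertaining to follow up colonoscopy or flexible sigmoidoscopy" "will be used as a comparator group for a diagnostic sensitivity / specificity analysis". No other accuracy analysis is named.

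Section 6 (Statistics and data analysis) adds only the software and that data "will be analysed using standard univariate statistical models". It also says that the data will be the basis of a power calculation for later studies.

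The documents do not give the Mayo version or range, a cut-point, an ordinal or agreement method, or a request that the follow-up endoscopist record a Mayo score.

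**The concern.** Severity is a question of degree. Sensitivity and specificity answer a question of presence or absence, so they apply to an ordered score only after it has been cut in two. This has three consequences.

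- **Lost information.** Every grading error that stays on one side of the cut counts as correct. Those errors are part of what the severity objective asks about.
- **An open choice.** The result depends on where the cut falls. With none stated, nothing prevents the choice from being made once the results are known.
- **A comparator that may not match.** If the follow-up report carries no Mayo grade, the graded comparison cannot be made for that patient, and this is hard to repair after the examination.

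At stake are the pilot estimate for severity and its use in sizing the next study.

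**Working it through.** **1. Inputs.** Section 2.1 states: "The study aims to recruit 100 patients into the pilot study". It gives no derivation, no number of flare patients and no number expected to have follow-up endoscopy, so there is no planned figure to reproduce. The calculations below are illustrations. The four levels (0 to 3), the 40 patients, the grade mix and the error rates are assumptions.

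**2. Worst case, with no error crossing the boundary between grades 1 and 2.**

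| Endoscopy grade | LumenEye 0 | 1 | 2 | 3 | Total |
|---|---|---|---|---|---|
| 0 | 4 | 2 | 0 | 0 | 6 |
| 1 | 4 | 4 | 0 | 0 | 8 |
| 2 | 0 | 0 | 8 | 6 | 14 |
| 3 | 0 | 0 | 4 | 8 | 12 |
| Total | 8 | 6 | 12 | 14 | 40 |

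- Exact agreement: (4 + 4 + 8 + 8)/40 = 24/40 = 60%.
- Chance agreement: (6×8 + 8×6 + 14×12 + 12×14)/1600 = 432/1600 = 0.27. Unweighted kappa = (0.60 − 0.27)/(1 − 0.27) = 0.45.
- Weighted kappa = 1 − (observed mean disagreement)/(mean disagreement expected by chance). All 16 errors are by one grade, so the observed mean is 16/40 = 0.40 under either weighting.
 - Linear: expected 1896/1600 = 1.185, so kappa = 1 − 0.40/1.185 = 0.66.
 - Quadratic: expected 3712/1600 = 2.32, so kappa = 1 − 0.40/2.32 = 0.83.
- Cut at 2 or more: sensitivity 26/26, specificity 14/14.
- Cut at 3 or more: sensitivity 8/12 (67%), specificity 22/28 (79%).

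The same table gives perfect accuracy at one cut and 67% sensitivity at the next.

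**3. A less contrived case.** Take equal grades (25% each) and 30% one-level errors. Middle grades move up or down with probability 0.15 each, and end grades move inward with probability 0.30. Exact agreement is 0.70.

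| Cut | Sensitivity | Specificity |
|---|---|---|
| 1 or more | (0.85 + 1 + 1)/3 = 0.95 | 0.70 |
| 2 or more | (0.85 + 1)/2 = 0.925 | (1 + 0.85)/2 = 0.925 |
| 3 or more | 0.70 | (1 + 1 + 0.85)/3 = 0.95 |

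No cut now looks perfect, but the answer still depends on the cut. Linear-weighted kappa is 0.75 and quadratic 0.87.

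**4. If the best of the three cuts were chosen by Youden index (sensitivity + specificity − 1).** This was simulated with 10,000 runs and equal grades, under the errors of step 3 and under 30% one-level undergrading. The apparent index exceeds the true index at the chosen cut by about 0.05 to 0.07 with 40 scored pairs, 0.08 to 0.11 with 25, and 0.11 to 0.16 with 15.

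**5. Is an ordinal estimate feasible in a pilot?** Under step 3, the 95% sampling range of quadratic-weighted kappa is 0.73 to 0.96 with 20 pairs and 0.80 to 0.93 with 50. That is imprecise but usable.

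**The case against.** **It is a feasibility study.** Section 6 says so, accuracy is secondary, and severity is one of four targets. This stands, and it limits the consequence: no conclusion on safety or acceptance depends on the point. It does not remove it, because section 6 also names initial diagnostic performance as an aim and uses the data for later power calculations.

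**The comparator may well carry a Mayo grade.** Section 2.3 takes in all follow-up endoscopy data, and section 5 mentions a case report form that is not reproduced. So one cannot say that the comparator will go unscored. What holds is that the protocol text does not require the score.

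**A reader might infer that the cut will be picked after the data.** The documents do not say this. They give no cut, which leaves the choice open. The optimism in step 4 arises only if the best-performing cut is selected.

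**A reader might infer that the two LumenEye readings per patient will be pooled into one comparison.** Nothing says so. The paired readings could equally serve secondary outcome 1, the utility of remote assessment.

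**Perfect accuracy with 40% misgraded is contrived.** It is. It needs every error to avoid one boundary, and step 3 shows a milder picture.

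**Weighted kappa brings its own free choice.** On the table in step 2 the weights move it from 0.66 to 0.83. This stands, so the weights must be fixed too.

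**Differences between examinations may be disease change.** Section 2.1 brings in IBD patients who cannot get urgent endoscopy, and section 5 ties further investigation to clinical need. Scored pairs may be few and late. This stands, and the fix should record the interval.

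**Conclusion.** The point holds in limited form. Colitis severity is a stated accuracy target recorded on a graded score, and the only accuracy analysis named is binary. No cut is specified and no matching score is required of the comparator. The generic statement in section 6 does not repair this.

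The possible size ranges from the constructed worst case (26/26 and 14/14 with exact agreement of 60%) to a symmetric-error case in which sensitivity moves from 0.95 to 0.70 and specificity from 0.70 to 0.95 as the cut rises. Both rest on an assumed four-level score and assumed error rates, and the first also on an assumed 40 patients. The argument itself needs only that the score is ordered. This should be changed, but it does not threaten the primary outcome.

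**What to change.** In sections 2.3 and 6:

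- Ask the follow-up endoscopist to record a rectal Mayo score on the same stated scale, without sight of the LumenEye score where feasible. Record the date of each examination.
- For colitis severity, report the full LumenEye-by-endoscopy cross-table, exact and within-one-grade agreement, and weighted kappa with a 95% CI. State the weights in advance. Within-one-grade agreement should not stand alone: it is 40/40 in the worst-case table.
- Do this separately for the local and the remote reading, with one row per patient, and describe the results by interval between examinations.
- Keep sensitivity and specificity for cancer and polyps. If a colitis cut is also reported, fix it now.

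The cost is a few sentences, one extra score field with a date, and a little more analysis. No procedure or patient is added.
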